## LIST OF ABBREVIATIONS

A(1-7)	Angiotensin 1-7
A-II	Angiotensin-II
ABG	Arterial blood gas
ACE	Angiotensin-converting Enzyme
ACE2	Angiotensin-converting Enzyme 2
AE	Adverse event
ALT	Alanine aminotransferase
ARDS	Acute Respiratory Distress Syndrome
AST	Aspartate aminotransferase
ATC	Anatomical therapeutic chemical
AT1R	Angiotensin II receptor type 1
AUC	Area under the curve
BiPap	Bilevel positive airway pressure
BP	Blood pressure
C	Celsius
C max	Maximum concentration
CK	Creatinine kinase
CPAP	Continuous positive airway pressure
CO 2	Carbon dioxide
COVID-19	Coronavirus disease - 2019
C-RP	C-reactive protein
CTCAE	Common Terminology Criteria for Adverse Events
DSMB	Data Safety Monitoring Board
ECG	Electrocardiogram
ECMO	Extracorporeal membrane oxygenation
eCRF	Electronic case report form
EDC	Electronic Data Capture
EPO	Erythropoietin
FDA	Food and Drug Administration
FiO 2	Fraction of inspired oxygen
HR	Heart rate

ICF	Informed Consent Form
ICH	International Conference on Harmonization of Technical Requirements for Registration of Pharmaceuticals for Human Use
ICU	Intensive care unit
ICMJE	International Committee of Medical Journal Editors
ISF	Investigator Site File
IWRS	Interactive Web Response System
IRB	Institutional Review Board
IV	Intravenous
kg	Kilogram
LDH	Lactate dehydrogenase
µg	Microgram
MedDRA	Medical Dictionary of Drug Regulatory Activities
mg	Milligrams
mL	Milliliter
MM	Medical Monitor
mm	Millimeters
mM	Millimolar
mmHg	Millimeters of mercury
MTD	Maximum tolerated dose
MV	Mechanical ventilation
NCI	National Cancer Institute
NDA	New Drug Application
NO	Nitric oxide
NOAEL	No-observed adverse effect level
OA	Oleic acid
OSCI	Ordinal Scale for Clinical Improvement
PaO 2	Arterial partial pressure of oxygen
PBW	Predicted body weight
PEEP	Positive end expiratory pressure
pH	Hydrogen ion concentration

PI	Primary Investigator
PK	Pharmacokinetics
QTc	QT interval corrected for heart rate
QTcB	Correction of QT values using Bazett's Formula
QTcF	Correction of QT values using Fredericia's Formula
RAS	Renin angiotensin system
RBC	Red blood cell
RR	Breaths per Minute
RT-PCR	Reverse transcription polymerase chain reaction
SAE	Serious adverse event
SAP	Statistical Analysis Plan
SARS	Severe Acute Respiratory Syndrome
SBT	Spontaneous breathing trial
SC	Subcutaneous
S-D	Sprague-dawley rats
SHR	Spontaneously hypertensive
SMP	Safety Management Plan
SOB	Shortness of breath
SOC	Standard of care (system organ class also SOC)
SpO 2	Peripheral capillary oxygen saturation
TEAE	Treatment-emergent adverse event
TG+	Renin transgenic
TTP	Time to progression
Vt	Tidal volume
USP	United States Pharmacopeia
WBC	White blood cell
WCG IRB	Western IRB/Copernicus Group
WHO	World Health Organization

## PROTOCOL SYNOPSIS

Title:	A Phase 2 Trial to Evaluate the Safety, Tolerability, and Preliminary Efficacy of Intravenous USB002 to Treat Patients with Respiratory Distress due to COVID-19 Infection
Sponsor:	US Biostest, Inc.
Study number:	USB002-2020-001
Phase:	Phase 2
Study objectives:	
Parts 1 and Part 2:
 

• To determine the safety and tolerability of USB002 in treatment of respiratory distress from coronavirus disease – 2019 (COVID-19) infection;

• To identify an early efficacy signal of USB002.

 
Part 1:
 

• To determine the maximum tolerated dose (MTD) of USB002 (up to 900 ug/kg/day).

 
Part 2:
 

• To determine preliminary efficacy of the USB002 MTD following up to 14 days of continuous infusion.

Study Endpoints:	
Safety of USB002 will be evaluated by:
 
The rate of occurrence and severity of Adverse Events (AEs) resulting from clinical changes (Day/Visit 1 to Day 28):
 

• Cardiovascular parameters, to include blood pressure (BP), heart rate (HR), 12-lead electrocardiogram (ECG), and requirements for inotropes and vasopressors;

• Laboratory parameters, to include kidney and liver function.

 
Preliminary efficacy of USB002 will be determined from start of treatment (Day/Visit 1) by time to peripheral capillary oxygen saturation (<math>\text{SpO}_2</math>) <math>\geq 94\%</math> on room air, sustained for at least 48 hours, through Day 28.
 
Additional preliminary efficacy assessments include the following, from start of treatment (Day/Visit 1) through Day 28:

	

• All-cause mortality at 60 days;

• Number of ventilator-free days;

• Number and proportion of subjects progressing from non-invasive to mechanical ventilation;

• Time of progression from non-invasive to mechanical ventilation;

• Proportion of subjects weaned from mechanical ventilation;

• Number of days of vasoactive agent usage;

• Time (days) to hospital discharge;

• Changes in clinical status, as defined by the 7-point ordinal scale.

Study design:	
This randomized, double-blinded, placebo-controlled study will be conducted in two parts:
 
Part 1 will escalate through four sequential doses of USB002 to determine the MTD. Part 2 will determine preliminary efficacy of the USB002 MTD dose identified in Part 1.
 
In Part 1, subjects will be randomized to receive Standard of Care (SOC) plus USB002 in up to 4 escalating doses (n=3) or SOC plus placebo (n=3) via continuous intravenous (IV) infusion, for up to 96 hours.
 
Dose escalation, assessment of progress and safety will be determined by a Data Safety Monitoring Board (DSMB) after review of the 96-hour clinical data. If toxicity is identified [evaluated according to the National Cancer Institute (NCI) Common Terminology Criteria for Adverse Events (CTCAE), version 5.0 criteria] at the lowest cohort level (90 ug/kg/day), DSMB may determine to de-escalate or halt the study. Escalation will continue until Part 1 enrollment is completed and the MTD is determined.
 
In Part 2, subjects will be randomized 1:1 to receive either SOC plus USB002 at the MTD established in Part 1 or SOC plus placebo infusion for up to 14-days.
 
For both Groups, when infusion is stopped/completed, whether prior to 96 hours, at the end of infusion (96 hours in Part 1, Day 14 in Part 2), or earlier, there will be a 24-hour observation period. If a subject stops treatment for any reason after the Visit 1 infusion begins, all attempts will be made to conduct the End of Treatment (Visit 5 in Part 1 and Day 16 in

	
Part 2 ) procedures (See Tables 2 and 3). End of Treatment (Visit 5 or Day 16) procedures may be conducted during the 24-hour observation period.
 
Infusion of USB002/placebo will be discontinued at any time if SpO2 is <math>\geq</math> 94%, sustained for at least 48 hours, on room air. Visits will continue up to Day 28, if subject is still hospitalized. The Day 28 and Day 60 follow-up visits will be conducted by phone (Telemed) if discharged.

Population:	

• 18 years of age or older; shortness of breath (SOB) and respiratory distress requiring oxygen due to COVID-19 infection;

• Up to 10 sites in the United States.

Sample size:	Part 1, up to 48 subjects.  Part 2, 30 subjects.

## 1. BACKGROUND INFORMATION

### 1.1. Investigational Product: USB002

USB002 is pharmaceutically formulated Angiotensin 1-7 [A(1-7)], a non-hypertensive derivative of Angiotensin-II (A-II) and is suspended in a vehicle as a sterile solution of USB002 (22.5 mg/ml) which is stable at room temperature for 90 days.

### 1.2. Nonclinical Experience with A(1-7)

The proposed treatment of patients with COVID-19-induced respiratory distress with USB002 is supported by animal models of Acute Respiratory Distress Syndrome (ARDS) (ventilator, oleic acid [OA] and sepsis induced), pulmonary hypertension, and fibrosis (Fleming 2005, Ishiyama 2004, Donoghue 2003, Imai 2005, Shenoy 2010, Walther 2011, Yamazato 2009, Zambelli 2015), which demonstrated that an imbalance between the angiotensin converting enzyme (ACE)/Ang-II/angiotensin II type 1 and the angiotensin converting enzyme 2 (ACE2)/Ang-(1-7)/Mas axis of the renin-angiotensin system (RAS) occurs in animals with lung disease.

Imai et al. (2005) showed that ACE2, which converts A-II to A(1-7) by cleavage of one amino acid, protects mice from ARDS induced by acid aspiration or sepsis. Shenoy et al. (2010) in rats showed positive effects in a pulmonary fibrosis model using lentiviral packaged A(1-7)-fusion genes or ACE2 cDNA. Overexpression of A(1-7) significantly prevented the associated negative effects of pulmonary fibrosis. Blockade of the Mas receptor abolished the beneficial effects of A(1-7), confirming the role of the Mas receptor and A(1-7) in protection of the lung. A(1-7) protects against ventilator induced ARDS in mice. A(1-7) attenuated the development of ARDS, as demonstrated by a normalization of the lung wet-to-dry weight ratio and a significant improvement in PaO2. A(1-7) also protects against OA-induced acute lung injury/ARDS in Sprague-Dawley rats as shown by changes in lung wet-to-dry weight ratio and reduced pulmonary vascular resistance (Yamazato 2009). Importantly, A(1-7) infusion was shown to improve pulmonary function, including prolonged improvement in oxygenation, reduction in inflammatory cells recruitment and reduction in lung fibrosis long term in an animal model of ARDS involving two insults, acid instillation and prolonged injurious ventilation. A(1-7) was effective even after delayed administration (Zambelli 2015).

### 1.3. Clinical Experience with USB002

The safety of USB002 has been demonstrated in seven clinical trials whose indications include breast cancer and chronic kidney disease. USB002 has also been studied in healthy volunteers. To date, 107 subjects have been treated with USB002 (referred to in studies as TXA127). Doses administered ranged from 2.5 µg/kg/day to 300 µg/kg/day administered as a subcutaneous (SC) dose for up to 28 days. USB002 has been well tolerated with no drug-related serious adverse events (SAEs) noted. A Phase 1/2 randomized, double-blinded, placebo-controlled study of intravenous (IV) USB002 given alone and with erythropoietin (EPO) was conducted in subjects with anemia associated

with end-stage renal disease. The trial had two arms: EPO plus USB002 at one of three (10, 25, or 50 µg/kg) IV doses, and EPO plus placebo three times weekly, administered following each hemodialysis session. No dose limiting toxicity (DLT) was observed in any dosing group. There were no differences between USB002 and EPO in adverse events (AEs) by body system.

## **1.4. Known and Potential Risks and Benefits to Human Subjects**

A favorable safety profile has been demonstrated with USB002 in preclinical toxicology studies. Single-dose and repeat-dose (4-week) toxicity studies were conducted in rats and dogs utilizing IV USB002 administration. The daily parenteral administration of USB002 to rats and dogs for one month at doses up to 1000 µg/kg/day did not affect clinical condition, body weight, or food intake. No changes in hematology parameters, serum chemistry values, or urinalysis were noted. In addition, there were no treatment-related histopathologic changes in any of the tissues or organs examined. Thus, the maximum no-observed adverse effect level (NOAEL) in rats and dogs following repeat-dosing was 1000 µg/kg/day. An acute IV study evaluated five male and five female mice that were injected with 100 mg/kg USB002. Clinical observations were recorded for 14 days. No treatment-related changes in clinical condition occurred. An acute IV irritation study was performed in 5 groups of three female rats each. The USB002 dose levels were 0.01, 0.1, 1.0, 10, and 100 mg/kg. A concurrent control group of three female rats received placebo. There were no deaths or gross necropsy findings, and no test article-related changes in body weight or clinical findings. An IV one-month study was conducted in rats (Crl:CD(SD)BR VAF/Plus) administered placebo or USB002 by slow bolus injection into a tail vein once daily for 4 weeks at doses of 0 (placebo), 0.01, 0.1, or 1.0 mg/kg. No test article-related effects were found for any toxicological parameter at any dose level. An IV one-month study of USB002 was conducted in beagle dogs by slow bolus IV injection once daily for 4 weeks at doses of 0 (placebo), 0.01, 0.1, or 1.0 mg/kg. No test article-related effects were found for any toxicological parameter at any dose level.

### **1.4.1. Potential Benefits to Human Subjects**

The RAS can be thought of as a hormonal system with 2 axes – the ACE/Ang-II/angiotensin II receptor type 1 (AT1R) axis (pathological arm) and the counter-regulatory ACE2/A(1-7)/Mas receptor axis (protective arm). The ACE/Ang-II/AT1R axis has now been implicated in the pathophysiology of the cardiovascular, renal, pulmonary, and central nervous systems (Nehme 2019). *In vivo*, Mas acts as a functional antagonist of the AT1R, thereby inhibiting these actions of Ang-II (Kostenis 2005). A(1-7) is the endogenous ligand of the Mas receptor and a member of the protective RAS.

COVID-19, like severe acute respiratory syndrome (SARS), binds to the cell surface protein receptor, ACE2, a member of the ACE2/A(1-7)/Mas axis. SARS pathology emerges, in part, due to the reduced ability of ACE2 to cleave A-II, a pro-inflammatory, fibrotic peptide, to A(1-7) (Zhou 2020). Ang-II is a potent vasoconstrictor that can increase lung injury and lung edema (Flemming 2005). A(1-7) counteracts the effects of Ang-II and mobilizes endogenous regenerative processes. Patients in intensive care for ARDS that

do not survive have reduced levels of A(1-7) compared to those that do survive. IV treatment with A(1-7) would not only reduce inflammation and oxidative stress but rebalance the RAS.

In a recent study of intensive care unit (ICU) patients with ARDS, increased serum levels of A(1-10) and reduced serum levels of A(1-7) at the time of admission in patients with this degree of dysregulation of angiotensin peptide metabolism did not survive, despite aggressive ventilator-assisted pulmonary therapy (Reddy 2019). Further, a recent publication showed that circulating Ang-II levels increased with increased COVID 19 viral load and reduced  $\text{PaO}_2/\text{FiO}_2$  levels (Lui 2020). In SARS-infected animals, increased levels of Ang-II were observed due to reduced ACE2 activity. In this study ACE2 cleaves Ang-II to A(1-7), thereby reducing the pathological activities of Ang-II and increasing the protective arm of the RAS through the ACE2/A(1-7)/Mas axis (Imai 2008).

In a bacterial model of pneumonia, treatment with A(1-7) reduced lung congestion 24 hours after infection (Soto 2020). Finally, in an unpublished study of bone marrow transplant following lethal irradiation, mice began to die due to an unplanned norovirus infection at day 3 after transplant. In mice that received donor cells from the saline treated animals and saline treatment after transplant, there was only 20% survival. In A(1-7) treated mice (both donor and recipient), there was 100% survival. This data show that A(1-7) not only improved sequelae secondary to infection but also prevented multiple organ system failure and death.

#### **1.4.2. Rationale for Clinical Trial**

COVID-19 may lead to respiratory distress which progresses from shortness of breath (SOB) requiring hospitalization and supplemental oxygen by nasal cannula, high flow oxygen delivered by a mask with <15 liters/minute of oxygen, bilevel positive airway pressure (BiPAP) with a mask that delivers high pressure 100% oxygen at 5 mmHg peak inspiratory pressure, and ultimately to intubation and assisted ventilation with a respirator. With an increasing number of hospitalized COVID-19 cases in the United States since January of 2020, COVID-19 presents an acute and urgent threat to global health security. Therapeutic interventions capable of reducing pulmonary distress would reduce the fatality rate, improve long-term outcomes, and free up scarce ICU resources.

Respiratory distress in untreated COVID-19 infected patients presents as a progressive continuum from SOB to cardiopulmonary collapse and death. It is diagnosed in symptomatic patients with bilateral lung infiltrates with confirmed positive tests for COVID-19. Without supportive therapy, pulmonary distress rapidly progresses to hospitalization where supplemental oxygen can be given by nasal cannula, high-flow mask, BiPAP mask, and eventually intubation and assisted ventilation. Overall, the physiological damage to cells and structures of the lung can begin within hours of exposure and progress within days (Fahy 2012). The pathologic hallmarks of COVID-19-induced pulmonary distress include neutrophilic alveolitis, hyaline membrane disease secondary to protein transudation and precipitation in the airspace, microthrombi secondary to the generation of procoagulant mediators as well as endothelial and epithelial injury. For these reasons,

there is considerable interest in the use of a A(1-7) to treat patients who have developed respiratory distress from COVID-19 infection (Soto 2020, Piero 2020, NCT 04332666).

From the above, the initial dose will be 1/10th the NOAEL in rats and dogs, and 1/1000th the maximum dose administered to mice, *i.e.*, 90 µg/kg/day.

## 2. STUDY OBJECTIVES AND PURPOSE

### 2.1. Study Objectives and Endpoints

The objectives of the study are twofold:

- To determine the safety and tolerability of USB002 in treatment of respiratory distress from COVID-19 infection; and
- To identify an early efficacy signal of USB002.

#### 2.1.1 Primary Objectives and Endpoints

The primary objectives of safety and tolerability of USB002 will be evaluated for rate of occurrence and severity of AEs resulting from clinical changes (Visit 1/Day 1 to Day 28): cardiovascular parameters, to include blood pressure (BP), heart rate (HR), 12-lead electrocardiogram (ECG), and requirements for inotropes and vasopressors; laboratory parameters, to include kidney and liver function.

The primary endpoint of preliminary efficacy will be demonstrating the difference between USB002 and placebo groups in time to peripheral capillary oxygen saturation ( $\text{SpO}_2$ )  $\geq 94\%$ , sustained for at least 48 hours, on room air through Day 28.

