#### **5.4.2. Visit Schedule Part 1**

AEs and concomitant medications will be reviewed and documented every day of hospitalization.

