### **6.4. Reporting Procedures**

#### **6.4.1 Adverse Event Reporting**

AEs will be captured from the start of USB002/placebo infusion until Day 28 or hospital discharge, whichever occurs last. Any AEs ongoing at Day 28 (or discharge) will be followed/assessed up to the Day 60 Telemed visit. No new AEs will be collected following discharge. SAEs (new or ongoing) will be followed and/or collected until Day 60.

All AEs (whether attributable to the study drug) occurring during the study observed by the Investigator or reported by the subject will be recorded on the eCRF. The following information will be recorded for all AEs:

- Event: name/condition/diagnosis/description;
- Onset and resolution time and/or date;
- Severity;
- Relationship to study drug (assessment by staff trained and authorized to

diagnose);

- Action taken;
- Seriousness.

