## 7. STATISTICAL CONSIDERATIONS

### 7.1 Statistical and Analytical Plans

Formal Statistical Analysis Plans (SAP) will be prepared for each part (1 and 2) of this trial and will be signed off prior to study database lock and prior to any unblinding procedures. Part 1 will detail parameters and interpretation of safety and efficacy signals for dose escalation randomization groups (SOC plus USB002 and SOC plus placebo). Part 2 will detail parameters and interpretation of preliminary efficacy outcomes of the

randomized groups. Any deviations to the planned analyses specified within the SAP will be justified in writing and presented in the final clinical study report.

In Part 1, the data summaries, which will be supported with by-subject listings, will focus on the dose group for SOC plus USB002 as compared to the SOC plus placebo as well as time in trial.

In Part 2, preliminary efficacy assessments will compare the endpoints for the two treatment groups for a signal of efficacy including: time without mechanical ventilation, all-cause mortality, survival at discharge, absence of respiratory failure, responders according to OSCI (see Appendix 1). Data relating to efficacy response will be listed and summarized by dose cohort and time point, as appropriate. On each measurement day, the worst OSCi score will be recorded. Since the efficacy objective of this study is to assess the preliminary efficacy signals, statistical inference (e.g. p value) from the efficacy analyses will be used to assess the strength of the efficacy signals, and will not be adjusted for multiple comparisons. Unless specified in the analyses of efficacy endpoints (see Section 7.2.1), missing data will not be imputed.

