#### **7.2.3.1. Adverse Events**

The number of subjects reporting, and number of events reported will be presented in frequency tables (overall, by intensity, by relationship and by outcome) for each dose cohort in each group. AEs of special interest will be presented separately. No specific AEs of interest are prospectively defined for the purposes of this study. AEs will be coded according to MedDRA (Vn. 23.1). All AE and abnormal laboratory variables will be assessed according to the CTCAE v5.0 grading system. Treatment-emergent adverse events (TEAEs) (events not present at baseline and worsened in severity following the start of treatment) will be presented. The following summaries will be provided at a minimum (the SAP will provide further details of summaries that will be provided):

- A summary of the number and percentage of patients reporting any TEAE/SAE;
- A summary of the number and percentage of patients reporting TEAEs according to severity;
- A summary of the number and percentage of patients reporting related TEAEs/SAE;
- A summary of the number and percentage of patients reporting TEAE/SAE by treatment group, preferred term, and system organ class;
- A summary of the number and percentage of patients reporting TEAE/SAE by treatment group, severity, and system organ class;
- A summary of the number and percentage of patients reporting TEAE/SAE by treatment group, by relationship to study drug, and system organ class; and
- A summary of the number and percentage of patients reporting a TEAE leading to withdrawal from study treatment by treatment group, preferred term, and system organ class.

Listings of the above will also be presented for the DSMB reviews on an ongoing basis; for each subject and for each TEAE, the worst severity recorded will be attributed and used in the by-severity summaries.

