7.2. Calculated Outcomes

The following are key endpoints derived from data captured at the sites via the EDC system. Complete documentation of the calculations and data manipulation required to go from the CRF database to the analysis database are contained in the companion documents – SDTM Programming Specification File (SDTM Spec) and ADaM Programming Specification File (ADaM Spec).

Outcome	Calculation	Comment
Study Day	= the days from Day 1 (Date of the First Study Infusion) to the event date	
Time in Trial (days)	= Study completion/withdrawal date – date of informed consent date + 1 day	
Time on Treatment	= Date of last infusion – Date of first infusion + 1	
Baseline value	= Value reported prior to the first study treatment	If multiple values collected prior to the first infusion, non-missing value closest to the date/time of the first infusion is considered as baseline value
Change from Baseline	= Value collected at time point (Visit) – Baseline value	
BMI	= $10000 * (\text{Weight in kg}) / (\text{Height in cm})^2$	Value will be rounded to keep one decimal point
Treatment Emergent Adverse Event (TEAE)	= No, if onset date/time AE is before the date/time of the first study infusion = Yes, otherwise	According to conservative rule, all AEs that cannot be determined as started before the first study infusion will be considered as TEAE

Outcome	Calculation	Comment
Time from baseline to achieving $\text{SpO}_2 \geq 94\%$ on room air	= Date of first achieving $\text{SpO}_2 \geq 94\%$ on room air – Date of first infusion + 1 = null if the subject did not achieve $\text{SpO}_2 \geq 94\%$ till study termination	
Number of ventilator-free days	= the number of days between Day 1 and Day 28 that subjects are both alive and free of mechanical ventilation	
Weaned from MV (Yes/No)	= Yes, if the subject was on MV and then weaned from MV through Day 28 = No, if the subject was on MV and kept using MV till Day 28 = null, if the subject did not use MV from Day 1 to Day 28	
Progressed to MV (Yes/No)	= Yes, if the subject progressed from non-invasive (at baseline) to MV on/before Day 28 = No, if the subject was keeping non-invasive till Day 28	
Time to Progression (TPP)	= First MV date – Date of first infusion + 1 = null, if the subject was keeping non-invasive till Day 28	
Time to hospital discharge	= Hospital discharge date – Study Day 1 + 1 = null if the subject was staying in hospital till Day 28	

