8.2.1. Adverse Events

Only treatment emergent adverse events (TEAEs) will be summarized. Summaries will be provided by dose level cohort with all placebo groups combined. Following summaries will be provided:

- Overview of TEAEs - include the total number of TEAEs, serious TEAEs, DLT, and TEAE leading to death
- TEAEs by MedDRA System Organ Class (SOC) and Preferred Term (PT)
- TEAEs by MedDRA SOC, PT, and severity
- TEAEs by MedDRA SOC, PT, and relationship to treatment
- TEAEs by MedDRA SOC, PT, and outcome
- Serious TEAEs by MedDRA SOC, and PT
- TEAE leading to death
- DLT.

All these summaries will include the counts and frequencies of events, and of subjects who had events.

All TEAEs will be listed by subject. Serious TEAEs, TEAEs leading to death, and DLTs will be listed separately.

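### The protocol contradicts itself on whether discharge ends AE capture, and the SAP's AE tables have no end date and no observation time; if post-discharge capture is absent or incomplete, shorter stays will show fewer non-serious AEs

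*Protocol*

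**What the plan says.** **Endpoint.** Protocol 2.1.1 states that "safety and tolerability of USB002 will be evaluated for rate of occurrence and severity of AEs" over Day 1 to Day 28. It gives no denominator.

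**AE tables.** Protocol 7.2.3.1: "The number of subjects reporting, and number of events reported will be presented in frequency tables", followed by numbers and percentages of patients. SAP 8.2.1: "All these summaries will include the counts and frequencies of events, and of subjects who had events". Neither uses time under observation.

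**End of AE capture.** The protocol has three statements:
- Section 6.4.1, opening sentence: capture runs to Day 28 or discharge, whichever is later.
- Section 6.4.1, same paragraph: "No new AEs will be collected following discharge".
- Section 3, under Parts 1 and 2: AEs that start after Day 28 are not captured; discharge is not mentioned.

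Both sections collect SAEs to Day 60.

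**Intensity of review.** In hospital, "AEs and concomitant medications will be reviewed and documented every day of hospitalization" (Protocol 5.4.2). After discharge, Part 1 subjects have weekly Telemed contact to Day 28 and do not return for site visits or procedures (Protocol 5.4.5).

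**Time variables.** Protocol 7.1 says that Part 1 summaries "will focus on the dose group for SOC plus USB002 as compared to the SOC plus placebo as well as time in trial". SAP 7.2 defines Time in Trial as "Study completion/withdrawal date – date of informed consent date + 1 day" and Time on Treatment as first to last infusion. SAP 8.1.1 summarises both by cohort. SAP 7.2 treats every AE not known to have started before the first infusion as a TEAE, with no latest onset date.

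**The concern.** Length of stay is a secondary efficacy endpoint that the drug is meant to change. If AE ascertainment depends on being in hospital, the number of AEs recorded depends partly on that endpoint. A group that goes home sooner would then show fewer non-serious AEs, and a lower percentage of subjects with an AE, at the same underlying rate.

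Nothing in the SAP would let a reader see or correct this. Time in Trial starts before the infusion and normally runs to about Day 60, after non-serious capture has closed. Time on Treatment covers at most the 96-hour Part 1 infusion. Neither measures the time over which AEs could be recorded.

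The open-ended TEAE definition adds a second mismatch. A serious event on Day 45 would enter the same tables as non-serious events collected to Day 28 or to discharge, although the endpoint window is Day 1 to Day 28.

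**Working it through.** The documents give no AE rate, length of stay or mortality figure, so there is nothing to reproduce. All inputs below are assumptions, used to see when the effect appears and how large it is.

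**1. The end-date statements for two subjects**

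| Subject | 6.4.1, opening sentence | 6.4.1, discharge sentence | Section 3 |
|---|---|---|---|
| Discharged Day 8 | capture to Day 28 | capture to Day 8 | capture to Day 28 |
| Still in hospital on Day 32 | capture to at least Day 32 | capture to at least Day 32 | capture to Day 28 |

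The statements disagree for early and for late discharge.

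**2. Observed days if capture stops at discharge**

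Assume exponential stay with median M, so the mean is m = M/ln 2, capped at Day 28. Expected observed days = m(1 − e^(−28/m)).
- M = 7: m = 10.10; 28 days is four half-lives, so 10.10 × (1 − 1/16) = 9.47 days.
- M = 14: m = 20.20; two half-lives, so 20.20 × (1 − 1/4) = 15.15 days.

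With the same rate r = 0.05 AEs per day in both groups, events per subject are 0.05 × 9.47 = 0.47 and 0.05 × 15.15 = 0.76. Dividing by observed days returns 0.05 in each.

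**3. Percentage of subjects with any AE**

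P = 1 − [(1 − q)/(1 + rm) + q], with q = e^(−28(1/m + r)).
- M = 7: q = 0.0625 × 0.2466 = 0.0154; P = 1 − (0.9846/1.505 + 0.0154) = 33%.
- M = 14: q = 0.25 × 0.2466 = 0.0616; P = 1 − (0.9384/2.010 + 0.0616) = 47%.

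**4. Partial detection after discharge**

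Let a share f of post-discharge AEs be detected. Then P = 1 − e^(−28fr) × [bracket from step 3 with r replaced by r(1 − f)]. Entries are median stay 7 v 14 days, with equal true rates:

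| Rate per day | f = 0 | f = 0.25 | f = 0.5 | f = 1 |
|---|---|---|---|---|
| 0.02 | 16% v 25% | 24% v 30% | 31% v 35% | 43% v 43% |
| 0.05 | 33% v 47% | 48% v 57% | 60% v 65% | 75% v 75% |
| 0.10 | 50% v 66% | 72% v 79% | 83% v 87% | 94% v 94% |

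The gap is about 8 to 16 points if discharge ends capture. It shrinks as detection improves and is nil when capture is complete.

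**5. How much remains if only death truncates**

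Simulate the ratio of mean observed time for 3 active v 11 placebo subjects, the same distribution in both groups, and count ratios outside 0.67 to 1.5.
- Observed time exponential with mean 15 days, minimum 1, capped at 28 (capture ends at discharge): about 43% of trials.
- Capture complete to Day 28, constant death hazard giving 10%, 20% or 30% mortality by Day 28: about 1%, 4% and 9%.

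**6. Is a rate too noisy to help?**

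Use the first setting of step 5 with 0.10 AEs per day in both groups. The ratio of events per subject-day falls outside 0.67 to 1.5 in about 53% of trials for 3 v 11, against 63% for events per subject. For a pooled comparison of about 11 v 10, the figures are about 33% and 44%. The rate is imprecise, but less so than the count.

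**The case against.** Several stronger readings are tempting, and the documents do not support them.

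- **A reader might infer that discharge does shorten AE observation, so the comparison is biased.** That rests on one of two conflicting sentences in Protocol 6.4.1. The other sentence, Section 3, the weekly calls and the AE row of the Part 1 schedule all fit capture to Day 28. With complete capture the effect largely goes (steps 4 and 5).
- **A reader might infer that the SAP departs from the protocol by replacing a rate with percentages.** Rate can mean a proportion, and Protocol 7.2.3.1 itself specifies counts and percentages. The SAP follows it.
- **A reader might infer that early death would pass for good tolerability.** SAP 8.2.1 tabulates serious TEAEs and TEAEs leading to death separately, and SAEs are collected to Day 60. The possible masking concerns mainly non-serious events after discharge.
- **A reader might infer that raw counts are compared across unequal groups without adjustment.** Subject-level frequencies are planned as well, which deals with group size.

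The consequence is also limited. Patients expected to stay under 96 hours are excluded (Protocol 4.2), so most of the infusion period should fall under daily review. Enrolment stopped at 21 subjects, no inference is planned, and all TEAEs are listed by subject.

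These points stand and lower the weight of the concern. They do not remove it. The end-date sentences conflict, no planned variable measures AE observation time, and agreement between groups under capture to Day 28 requires weekly calls to find as much as daily review. With no inference, readers will judge safety from these tables directly.

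**Conclusion.** The point holds in a conditional form, as an inexpensive improvement. What is certain from the documents is the contradiction over the end of AE capture, the absence of an upper limit on TEAEs against a Day 1 to Day 28 endpoint, and the lack of any AE observation time.

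Whether the tables mislead depends on two things the documents do not settle: which end-date sentence governs, and how complete detection is after discharge. At 0.05 AEs per day and median stays of 7 and 14 days, the spurious difference is 14 points if capture stops at discharge, about 9 points if a quarter of later AEs are found, and nil if all are found. These figures rest on a constant AE rate, exponential stays and identical true rates, all of them assumed. The documents do not show that a bias exists in this trial, or which group it would favour.

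**What to change.** 1. **Protocol 6.4.1 and Section 3:** reconcile the sentences on when AE capture ends, for discharge both before and after Day 28, and state in the SAP the rule that was applied.
2. **SAP 7.2:** define AE observation time as first infusion to the earliest of death, consent withdrawal, loss to follow-up and Day 28, and also discharge if discharge ends capture.
3. **SAP 8.2.1:** restrict the Day 1 to Day 28 TEAE tables to onsets in that window, and list later SAEs separately.
4. **TEAE overview:** summarise observation time by group. Add TEAEs and serious TEAEs per 100 subject-days for pooled active, placebo and, descriptively, each dose cohort. If AEs are collected after discharge, split the rates into in-hospital and post-discharge time.
5. **Keep** the planned counts and percentages. Do not add rates to the SOC and preferred-term tables, which are too sparse.

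**Cost.** One derived variable and a few overview rows. The plan already calls for AE onset, first infusion, discharge, death and withdrawal data, and Telemed contacts are entered in the EDC; a last-contact rule is needed for subjects lost to follow-up. The downside is that a rate assumes a roughly constant hazard and is very imprecise in cohorts of 3, so it supplements the percentages and should carry that caveat.
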